In the last two decades, the evolution of neuroimaging modalities in the field of neurourology has provided a new frontier of research. In 1998, Blok et al. studied normal female micturition in 10 subjects with CNS PET imaging. Increased blood flow was demonstrated in the right dorsal pontine tegmentum and the right inferior frontal gyrus. (1) Other investigators have incorporated the use of fMRI to examine brain region activation during bladder filling (2), and voluntary pelvic floor muscle contractions (3, 4). Furthermore, others have published fMRI evidence of cortical neuroplastic changes after pelvic floor muscle training and biofeedback therapy for stress urinary incontinence (5). Krhut et al. used fMRI to preliminarily examine brain activity during bladder emptying, localizing areas in the parahippocampal gyrus, anterior cingulate gyrus, inferior temporal gyrus and inferior frontal gyrus during micturition (6). Our project to evaluate the normal healthy female subjects with concurrent urodynamics and fMRI has yielded valuable information regarding anatomical locations neuronal control in micturition. We completed the first part of current project (IRB [Pro00005508](#)) in July of 2013 and have reported our results at multiple scientific meetings. The manuscript is in progress currently. This would be second report in the literature on micturition with simultaneous UDS and fMRI and higher number of subjects. In summary all of our ten subjects were able to void while supine. Each patient was able to void at least three complete voiding cycles within the fMRI scanning phase, with time to initiate voiding and cystometric capacity as factors in total number of voiding cycles.

Group analysis of the patients (since all were able to void) yielded consistent areas of activation during the initiation of voiding (asterisks, Figure 1). These included regions for motor control (cerebellum, thalamus, caudate, lentiform nucleus, red nucleus, supplementary motor area, postcentral gyrus), emotion (anterior and posterior cingulate gyrus and insula), executive function (left superior frontal gyrus), as well as the parahippocampal gyrus, precuneus, cuneus, occipital lobe (visual stimulus), and a focal region in the midbrain.

[figure not shown]

Figure 1.

Brain Control of Voiding

Preliminary correlation-interaction network analysis of 5 representative subjects were performed with the voxel-intensity time courses for a subject depicted (Figure 2A). This yielded spring-embedded network layouts that for each subject exhibited a small-world structure of focal clusters with short-range interactions connected by long-range edges (Figure 2B). A 3-D representation of cluster connectivity (Figure 2C) showed various clusters in the cerebellum connected to clusters in parietal, frontal and temporal lobes and to clusters in the limbic system mainly via the medial posterior brain regions (e.g. posterior cingulate).

[figure not shown]

Figure 2

Now that we have a better understanding of normal healthy micturition we plan to study brain activity in patients with neurogenic bladder (such as patients with multiple sclerosis) and voiding dysfunction. There is no similar report in the literature. In patients with multiple sclerosis, urinary symptoms are common sequel: urgency, urge incontinence, frequency, urinary retention (7, 8). These patients often undergo urodynamic testing and abnormalities are seen in almost all symptomatic cases. Common findings include neurogenic detrusor over-activity, detrusor sphincter dyssynergia and detrusor hypocontractility.

Clinical correlation between women with these chronic urologic problems and new discoveries at the level of CNS activity will give a better understanding of this disorder, leading to the development of more effective diagnostic and treatment modalities.

In addition the literature lacks any data regarding sensory effects of bladder medications used for neurogenic detrusor overactivity(NDO) or overactive bladder(OAB). A common and FDA approved treatment for these patients include use of Botulinum toxin A injected in the bladder. This is a routine

Brain Control of Voiding

management for urinary symptom control in these patients. Despite having knowledge and data that Botulinum toxin A decreases the bladder contractility we have no human data how it affects the sensory efferent fibers to the brain and decreasing urgency and frequency. Our platform is a perfect model to study the effects of botulinum toxin A on sensory efferent fibers of the bladder and correlate that to the centers in the brain that respond to urgency and frequency. Thus we propose that patients who based on their clinical needs and exams are candidates for intravesical botulinum toxin A and have been a candidate in our study to have another fMRI with concurrent UDS about 8 weeks following their intravesical botulinum toxin A injection.

Purpose and Objectives

To perform functional MRI neuroimaging and data analysis on female subjects diagnosed with voiding dysfunction or neurogenic bladder during the act of micturition. Our goal with this pilot study is to determine whether BOLD signal changes on fMRI during voiding are substantial for data analysis. If so, data analysis will yield specific regions of the brain that are activated and/or deactivated during voiding. The second objective of this study is to determine whether concurrent urodynamics data gathered in the scanner can be correlated to fMRI data in order to elucidate simultaneous bladder function measurements with BOLD signal measurements.

Second objective of this study is to evaluate the sensory effects of intravesical injection of botulinum toxin A used for neurogenic detrusor activity.

Risk Category

(45 CFR 46.406) Category 3: Research involving greater than minimal risk and no prospect of direct benefit to the individual subject, but likely to yield generalizable knowledge about the subject's disorder or condition.

Research Design

This is a pilot observational study in which brain activity will be observed via fMRI during simultaneous urodynamics testing. This study will examine the blood-oxygen-level-dependent (BOLD) signals during fMRI of the brain of subjects diagnosed with neurogenic bladder or dysfunctional voiding. BOLD signals are an indirect measure of neural activity that can be identified on fMRI. There are no known risks to a subject's fetus. There is no known teratogenic risk associated with urodynamics or fMRI. Patients will be screened with a urine pregnancy test at enrollment. Patients with a positive pregnancy test will be excluded from the study. As a pilot study, 50 subjects will be recruited to investigate the feasibility of the study. There is no control group because this study involving human subjects with both urodynamic and fMRI testing is complex, time-consuming, and expensive. In addition we can already use our data for the past two years on normal healthy females as our control. Furthermore, no investigator has published previously regarding simultaneous urodynamics and fMRI in patients with neurogenic bladder and dysfunctional voiding. Subjects diagnosed with neurogenic bladder (e.g. MS) and dysfunctional voiding would have already undergone baseline urodynamic studies as part of their routine care and will proceed to concurrent fMRI and urodynamics testing.

Brain Control of Voiding

Inclusion Criteria for subjects with voiding dysfunction and neurogenic bladder:

- Women ages 18 years or older
- Primary language is English
- Presence of lower urinary tract symptoms (urinary frequency, urgency, urge incontinence or difficulty emptying)
- Presence or history of neurologic illness or injury (spinal cord injury, spina bifida, Parkinson's, major spine surgery, multiple sclerosis, or other neurological disorders) and dysfunctional voiding.
- Performed baseline clinic urodynamics testing as part of routine urologic evaluation of voiding dysfunction within 24 months of scanning (if not done, will be performed as part of the study).

Exclusion Criteria for subjects with voiding dysfunction:

- Male
- Patients without lower urinary tract symptoms (urinary frequency, urgency, urge incontinence or difficulty emptying, etc)
- Positive urine pregnancy test at enrollment (There are no known risks to a subject's fetus. There is no known teratogenic risk associated with urodynamics or fMRI)
- Presence of active and symptomatic urinary tract infection
- Exclusive use of indwelling urethral or suprapubic catheter or other methods of urinary diversion
- Severity of neurologic illness: severe immobility, severe dyscoordination, cognitive impairment

STUDY PROCEDURE

Subjects will be recruited via bulletin board advertisement, web site and word of mouth.

All procedures are investigational. None of the following are part of standard clinical care.

There are no known risks to a subject's fetus. There is no known teratogenic risk associated with urodynamics or fMRI. Patients will be screened with a urine pregnancy test at enrollment and before fMRI scanning. Patients with a positive pregnancy test will be excluded from the study.

Procedure Visits:

1) Informed Consent and Enrollment

Patients will be screened with a history and physical, urinalysis and urine culture, and urine pregnancy test. Subjects will also be asked to fill out the following questionnaires: Urogenital Distress Inventory (UDI-6), Incontinence Impact Questionnaire (IIQ-7), and the Hamilton Anxiety Rating Scale (HAM-A). Patients will also be asked to fill out an fMRI safety screening questionnaire and demographics form.

After informed consent and enrollment, subjects will be scheduled for one or two visits:

2) Clinic Urodynamics Visit

Subjects diagnosed with neurogenic bladder or dysfunctional voiding have already undergone clinic urodynamics based on routine clinical care and will proceed to step 3. If there is a patient that would need a urodynamic study they will be instructed to arrive at The Methodist Hospital Department of Urology. This visit will consist of multichannel urodynamics in the clinic setting, so subjects can acclimate to the

Brain Control of Voiding

catheters and the testing situation. This visit will be 100% research. However, the test performed is one used by the urology clinic in daily clinical care. While the data collected will be for study use only, there is nothing experimental about the urodynamics procedure. Prior to catheter insertion, a dip stick urinalysis is performed to exclude bacteriuria.

3) fMRI Scanning Visit

The second visit will be the fMRI scanning session at the Methodist Hospital. Subjects will be instructed to arrive 30 minutes prior to scanning. Subjects will have a dip stick urinalysis performed and a urine pregnancy test to confirm that they are not pregnant prior to the insertion of the catheters and the MRI. Urodynamics catheters will be inserted. After task instruction, subjects will be placed in the scanner. Task instruction consists of giving subjects directions to hold their urine, relax their pelvic muscles, and void will be conveyed to them via instructions printed on a screen they will see while in the scanner. Patients will also be instructed to squeeze a bulb in their hand if they experience claustrophobia or discomfort, and want to be removed from the scanner. Scanning will then begin.

After standard localizer and structural scans, the functional sequence and urodynamics will start. The bladder will be filled with sterile saline, as per urodynamics procedure. Subjects will be instructed (visually using a projection screen and mirror, standard procedure for the HNL) to hold their bladder, and then view a fixation cross for 30 seconds. They will be asked to indicate, via finger button, when their bladder is full. Subjects will then be instructed (again using a projection screen and mirror) to relax their pelvic floor muscles, and then to urinate. The experiment will conclude with the subject pressing the finger button to indicate they are finished urinating. At that point an instruction to relax will appear and then be replaced by a fixation cross that the subject will view it for 30 seconds and the experiment will be complete. The urodynamic and scanning cycle may be repeated up to 5 cycles.

4) repeat fMRI scanning visit:

This visit would only apply to the patients that clinically were a candidate for intravesical injection of botulinum toxin A and went on receiving it as a part of their routine care. If they agree, we would recruit them for a repeat fMRI scan just as detailed above about 8 weeks (+/- 4 weeks) following their botox injection. Urogenital Distress Inventory (UDI-6), Incontinence Impact Questionnaire (IIQ-7), and the Hamilton Anxiety Rating Scale (HAM-A) will be re-obtained at this visit.

Sample Size

How many subjects (or specimens, or charts) will be used in this study?

Local: 50 Worldwide: 50

Please indicate why you chose the sample size proposed:

This is a pilot study. These experiments are novel, as there is currently no similar study in the literature. There is no way to predict numbers required in order to find statistically variations between arms of each experiment. Pilot data from this study will aid in powering future studies on the same topic. This study involving human subjects with both urodynamic and fMRI testing is complex, time-consuming, and expensive. Furthermore, no investigator has published previously regarding simultaneous urodynamics

Brain Control of Voiding

and fMRI. This protocol is for a feasibility study. Once the feasibility of our model is established, we can work on studying control groups.

Data Analysis

Provide a description of your plan for data analysis. State the types of comparisons you plan (e.g. comparison of means, comparison of proportions, regressions, analysis of variance). Which is the PRIMARY comparison/analysis? How will the analyses proposed relate to the primary purposes of your study?

The data analysis will be similar to other data analytic strategies carried out in the laboratory. It requires fairly complex analysis techniques and is thus difficult to summarize without going into lengthy details. Briefly, our data analysis will be as follows: We have made extensive use of a general linear model in analyzing and designing our fMRI experiments. To compare data from different subjects, the scan data from each subject must be transformed into a standard anatomical framework. We follow the approach of Frackowiak et al (1997), which analyzes the brain into small local volumes or “voxels”. The fMRI signal from each voxel is then subjected to the following transformation steps:

Analysis Step 1: Spatio-temporal normalization to a standard brain map, and smoothing to improve the signal-to-noise ratio.

Analysis Step 2: Statistical analysis to determine the significance of the activity measured at each voxel. We use an established statistical framework [K.J. Friston, et al., Human Brain Mapping 2, 189-210 (1995); K.J. Friston, A.P. Holmes, K.J. Worsley, Neuroimage 10, 1-5 (1999)] in terms of a general linear model, which incorporates and formalizes the independent explanatory variables in our experiment. Given the variance of each parameter, we can construct a t-statistic as a measure of the significance of differences in the parameters estimated from the different experiments, at different voxels, or in different subjects. In practice, we construct a statistic out of a particular linear combination of the parameters that describes a quantity of interest. To express this mathematically, we define a contrast vector that specifies a linear combination of parameters. Then the t-statistic is the quantity of interest divided by its standard error. When we calculate a t-statistic at each voxel in an imaged brain, measuring the significance of a difference between parameters from different subjects or different experimental conditions, the resulting set is called a statistical parametric map. We use such maps to determine areas of significant activation in the brain during presentation of stimuli or performance of the task.

A linear regression analysis will also be employed to look for covariance of behavioral variables with observed brain activity. For instance, the degree of preference for an image or the amount of prior exposure to the stimulus can be entered into the analysis as explanatory variables for the brain activation. In this case, the degree to which behavioral variables cause linear changes in brain activity can be illustrated by fitting the estimated response to the observed time series of dynamic blood flow in the brain. The regions identified in this type of analysis will be used to generate “regions of interest”, smaller areas of voxels that can be analyzed without making assumptions regarding the underlying hemodynamics. In this analysis, the raw change in magnetic signal can be read out and compared across any variable of interest.

Brain Control of Voiding

Potential Risks/Discomforts

Risks with Pregnancy:

There are no known risks to a fetus associated with urodynamics or fMRI. Regardless, pregnancy is an exclusion criterion. Every subject will be screened with a urine pregnancy test at enrollment. Subjects with a positive pregnancy test will be excluded from the study.

Urodynamics Testing:

Urodynamics studies involve invasive catheterization of the urethra and the rectum. The risks and discomforts of urodynamics testing include: discomfort in the bladder, urethra and rectum at the time of testing. The subject may also experience dysuria for 12 hours after testing. Another risk is that of urinary tract infection (UTI). All subjects undergoing urodynamic testing will be screened for UTI prior to testing. Patients will be given information regarding the symptoms and signs of UTI and asked to call the urology investigator's office if they have any of the symptoms after testing. If a UTI is present, it will be treated.

fMRI:

Movement or heating of metallic implants is a potential risk, and so subjects will be screened to exclude people with metallic implants. Some individuals experience claustrophobic reactions in the scanner. Subjects will be informed of this prior to the study, but because it is difficult to predict who will have such a reaction, this is not a specific exclusion criterion. Any subject experiencing claustrophobia will be removed from the scanner immediately. There is no invasive component to this study, such as IV catheters. Therefore, bruising or infection are not risks.. The Siemens 3 T scanner has been approved by the FDA. However, there may be additional risks associated with scanning at 3 T compared to the conventional clinical scanners in the 1.5-2.0 T range. These include: 1) Effect of the static field. There is no conclusive evidence for irreversible or hazardous bioeffects to acute, short term exposures of humans up to 2.0 T (Shellock and Kanal, 1996). Studies have indicated some side-effects at 4.0 T, namely unusual sensations including nausea, vertigo, and metallic taste (Schenk 1991). However, there is no evidence that this is either irreversible or harmful. If subjects experience unusual sensations, they will be withdrawn. 2) Effect of the gradient field. MRI operates by rapidly changing small additional fields, called gradients. This will induce small electrical currents in any conductor, and this could theoretically induce mild peripheral nerve stimulation. However, this is not substantially different at higher magnetic fields since the gradients are separate from the main magnet. There is no evidence that the effect of the gradients is any different at 3 T than at 1.5 T. However, if subjects experience peripheral nerve stimulation, e.g. tingling or twitching, they will be withdrawn. 3) Effect of the RF electromagnetic field. The higher magnetic field strength requires that higher RF frequency pulses are used to excite the protons in the subject's brain.

QUESTIONNAIRES:

Completing the questionnaires may cause you to have or to experience some level of emotional discomfort due to the personal nature of the questions. The study doctor and staff will maintain a professional and caring attitude while administering the questionnaires.

Brain Control of Voiding

REFERENCES

1. Blok BF, Sturms LM and Holstege G: Brain activation during micturition in women. *Brain*. 121 (Pt 11): 2033-42, 1998.

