Appendix D: Schedule of Events

Activity**	Screening Phase	Study Phase		Only if indicated 8 weeks after BOTOX inj.
		Visit 2	Visit 3	
	Screen and Enroll Visit 1	Visit 4		
Patient History	X			
Physical Exam	X			
Medication Review	X			
Consent for Study	X			X
UA and UC+S	X	X ¹	X ¹	X
Urine Pregnancy Test	X		X ²	X
UDI-6 questionnaire*	X			X
IIQ-7 questionnaire†	X			X
HAM-A rating scale‡	X			X
fMRI Screening Form	X			
Urodynamics Testing (part of routine care in this population)		X ³	X	X
fMRI Scanning			X	X

**NOTE: All activities are RESEARCH Related.

1 – The urine analysis done at visit 2 and visit 3 are dipstick analysis only and no culture is performed

2 – The urine pregnancy test done at visit 3 is a kit that shows immediate results of positive or negative

3 -- Only for the patients who have not had a UDS in the preceding 24 months

UA: urine analysis. UC: Urine culture & Sensitivity. *UDI-6: Urogenital Distress Inventory questionnaire. † IIQ-7: Incontinence Impact questionnaire. ‡HAM-A : Hamilton Anxiety rating scale.

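### The botulinum toxin objective rests on one group scanned before and after injection, so a BOLD change cannot be attributed to the injection, and drug changes between the scans are not recorded

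*Combined protocol and SAP*

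**What the plan says.** The background section presents the scanner set-up as suited to this question: "Our platform is a perfect model to study the effects of botulinum toxin A on sensory efferent fibers of the bladder". Purpose and Objectives then lists it as an aim: "Second objective of this study is to evaluate the sensory effects of intravesical injection of botulinum toxin A used for neurogenic detrusor activity". Neither place limits what may be attributed to the injection.

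Study Procedure, item 4, restricts the repeat scan: "This visit would only apply to the patients that clinically were a candidate for intravesical injection of botulinum toxin A". The woman must also have received the injection in routine care and agree to return. The rescan falls 8 weeks after injection, plus or minus 4. No interval from the first scan to the injection is stated.

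Research Design describes the study type: "This is a pilot observational study in which brain activity will be observed via fMRI during simultaneous urodynamics testing". On controls it says "There is no control group because this study involving human subjects with both urodynamic and fMRI testing is complex, time-consuming, and expensive" and adds "In addition we can already use our data for the past two years on normal healthy females as our control". The background reports ten such healthy women and describes no second scan for them.

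In Appendix D, the row "Medication Review" has one mark, at Visit 1. UDI-6, IIQ-7 and HAM-A are marked at Visits 1 and 4. The demographics form in Appendix E also asks for current medications, but Study Procedure, item 1, places it at enrollment.

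Data Analysis gives a general linear model with voxelwise t-statistics on contrasts. It names no paired before/after contrast and no handling of scan order, elapsed time or drug changes.

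**The concern.** The objective asks about the effect of the injection, but the design yields only the change in women who were injected. Each of them is injected between her first and second scans, so injection and second session always coincide. Several other things can move the BOLD response between sessions: familiarity with the scanner and the in-scanner task, time and disease course, a return towards usual levels after injection prompted by clinical need, and bladder drugs started, stopped or altered around the injection. The plan does not record the last of these.

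At stake is the conclusion for this objective. A reader shown a significant before/after map under the present wording would naturally take it as a drug effect on sensory pathways, and the data could not support that. If drug changes are not recorded at the repeat visit, they may not be reliably recoverable later.

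**Working it through.** The documents give no alpha, power, effect size or SD for this comparison, so there is no planned figure to reproduce. The main argument is about what the design can identify. The arithmetic only illustrates it.

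**1. What the comparison estimates.** For an injected woman,

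observed change = injection effect + second-session effect + time or disease course + regression to the mean + effect of drug changes.

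One group scanned twice gives the mean of the sum, not its parts.

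| Possible source of separation | What the plan provides |
|---|---|
| Uninjected patients rescanned | None (Study Procedure, item 4) |
| Healthy women rescanned | None described (background; Research Design) |
| Record of drugs at second scan | None (Appendix D; Appendix E form used at enrollment only) |
| Fixed interval from first scan to injection | None stated |
| Model term for order, time or drugs | None (Data Analysis) |

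**2. Which part of the second exposure is new.** The inclusion criteria require clinic urodynamics within 24 months of scanning, or done in the study. The risk section says urodynamics involves urethral and rectal catheterization. Every woman has therefore had the catheters before her first scan. What differs between first and second scan is familiarity with the scanner and the in-scanner task.

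**3. Illustration.** Assumptions: zero injection effect; a shift from other causes of d SDs of the within-woman change; a two-sided 5% paired t-test; n rescanned women. The rejection probability is

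P(|T| > t(0.975, n − 1)), with T noncentral t on n − 1 df and noncentrality d√n.

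For n = 10 and d = 0.3, the critical value is 2.262, the noncentrality is 0.3 × √10 = 0.949, and the probability is 0.136. For n = 20 and d = 0.5, the critical value is 2.093, the noncentrality is 0.5 × √20 = 2.236, and the probability is 0.565 (0.5645 before rounding, so 56%).

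| n rescanned (assumed) | d = 0 | d = 0.2 | d = 0.3 | d = 0.5 |
|---|---|---|---|---|
| 10 | 5.0% | 8.8% | 13.6% | 29.3% |
| 20 | 5.0% | 13.6% | 24.7% | 56.5% |
| 50 (every participant) | 5.0% | 28.4% | 54.8% | 93.4% |

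The rate rises with n, so more recruitment does not cure the problem.

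**4. Scale.** d is in SDs of the within-woman change. If a shift s is instead expressed in SDs of a single-scan response, with equal SDs at the two scans and scan-rescan correlation r, then d = s / √(2(1 − r)). The two scales agree only at r = 0.5. With s from 0.3 to 0.5 and r from 0.2 to 0.8, the rates run from 10% to 61% for n = 10 and from 17% to 92% for n = 20.

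**The case against.** The strongest reply is that the study is openly an uncontrolled pilot. Research Design says there is no control group and why, and the Sample Size section calls it a feasibility study and defers control groups. The objective says *evaluate*; it does not promise to establish an effect. HAM-A and the symptom questionnaires are repeated at the second scan, and Data Analysis foresees regression on behavioral variables, so some covariates would be available. All women have had urodynamics, and the in-study clinic visit is partly meant for acclimatization.

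Much of this stands. A reader might infer that the protocol asserts a proven drug effect, or that any change will be published as one. The documents contain no such assertion and no reporting rule. The problem is that the wording invites that reading and nothing limits it. A reader might also infer that the second scan is the second encounter with the catheters. It is not, as shown in the working. And the absence of a stated interval from first scan to injection does not show that the gap will be long.

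The reply does not remove the mismatch. Disclosing that there are no controls is not the same as limiting the inference. HAM-A rates general anxiety and is assigned no role in this comparison. The clinic visit involves no scanner. No repeated measure covers drug changes.

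A tempting repair is to model cycle number within a session (up to 5 cycles), or to compare first cycle with first cycle. Cycle number estimates a trend within a session. It does not identify the change from first to second session, which remains fully aligned with injection. A first-cycle comparison keeps the scan-order difference. The background also links the number of cycles to bladder capacity and time to initiate voiding, which the injection could itself alter.

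**Conclusion.** The point holds as a limit on attribution. As written, the plan cannot separate the injection from second exposure to the scanner and task, elapsed time, regression to the mean, or unrecorded changes in bladder drugs. This follows from who is rescanned and what is recorded, and depends on no assumed number.

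The size is not known. The figures of 14% to 29% (n = 10) and 25% to 56% (n = 20) rest on an assumed shift of 0.3 to 0.5 SD of the within-woman change and on assumed numbers rescanned. A reader might take them as a forecast of this study's false-positive rate. The documents do not support that: they give neither input, and do not show that any of these influences occurs.

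The change is worth making but is no reason to stop the study. It concerns one objective of a pilot, and the aim of mapping brain activity during voiding at the first scan is unaffected.

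**What to change.** 1. In Purpose and Objectives, restate the aim as: *describe the within-woman change in BOLD and urodynamic response after injection*. Add that the change is not attributable to the injection alone, and bring the background sentence on the platform into line. In Data Analysis, specify paired contrasts in women with both scans.
2. In Appendix D, mark Medication Review at Visit 4. Report the paired results with and without women whose bladder drugs changed between scans.

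Do not offer cycle-number or first-cycle analyses as a remedy for habituation between sessions.

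The cost is some wording, one extra mark in the schedule, a small amount of data collection and a minor additional analysis. The downside is a weaker claim, and excluding women whose drugs changed will shrink an already small sample. A rescanned uninjected group would allow a stronger claim, because any shift common to both groups would cancel. It would need real resources, though, and without randomization would still leave confounding by indication. It is not needed for this correction.

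### On-screen text and a button press precede every void, and the analysis plan does not say how they are separated from voiding, so stimulus-related activity may appear in the voiding map

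*Combined protocol and SAP*

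**What the plan says.** Study Procedure, 3) fMRI Scanning Visit, sets the order of events. Subjects are told by projected text "to hold their bladder, and then view a fixation cross for 30 seconds". During filling, "They will be asked to indicate, via finger button, when their bladder is full". Then: "Subjects will then be instructed (again using a projection screen and mirror) to relax their pelvic floor muscles, and then to urinate". At the end, "The experiment will conclude with the subject pressing the finger button to indicate they are finished urinating", after which a further relax instruction is shown and gives way to 30 seconds of fixation. "The urodynamic and scanning cycle may be repeated up to 5 cycles". A fixation cross is said to follow the hold text and the final relax text. Nothing says when the urinate text leaves the screen.

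Data Analysis, Analysis Step 2, uses a general linear model that "incorporates and formalizes the independent explanatory variables in our experiment". It does not list those variables. The contrast is described only as some linear combination of parameters, and the maps are said to show activation during stimulus presentation or task performance, without distinguishing the two. The covariates given as examples (image preference, earlier exposure to a stimulus) do not belong to this task.

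The opening background section reports the completed healthy series. Its areas active at the initiation of voiding include "precuneus, cuneus, occipital lobe (visual stimulus), and a focal region in the midbrain".

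**The concern.** The main product, under Purpose and Objectives, is a list of regions activated or deactivated during voiding. Text and a press come shortly before each void, while the only rest periods described show a fixation cross. If the model contains a void term and no text or press term, part of the response to the text can be credited to voiding. The healthy results show that activity the authors themselves ascribe to a visual stimulus did reach an initiation-of-voiding list. The occipital lobe is easy to recognise as visual; a stimulus or attention effect in a less obvious region would not be.

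The leakage can also depend on how soon flow follows the text. Women with difficulty emptying are eligible, and the background names time to initiate voiding as a factor even in healthy women. Research Design uses the healthy data as the control, and some women are rescanned after botulinum toxin. Hesitancy alone could then produce a difference from the healthy data or between two scans of the same woman.

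**Working it through.** The plan gives no figure to reproduce, so this is an illustration under stated assumptions.

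**From the documents:** the event order above, 30 s fixation periods, up to 5 cycles now, and at least three cycles per healthy woman.

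**Assumed:** TR 2 s; double-gamma response h(t) = g(t; 6) − g(t; 16)/6, where g is the gamma density; 30 s void; 3 cycles. Setting A has a 120 s fill, 4 s texts and a 5 s initiation window. Setting B has a 240 s fill, 3 s texts and a 10 s initiation window.

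**Step 1, leakage.** Let y be the signal of a region that responds only to text (text display convolved with h), and v the void regressor. Fit y = a + b·v + error. Leakage = b × max(v) / max(y), the spurious void response as a share of the peak text response.

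Setting A, void timed from flow, by delay from urinate text to flow:

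| Text and window | 0 s | 2 s | 5 s | 10 s | 20 s |
|---|---|---|---|---|---|
| Brief, 5 s initiation | 88% | 54% | 6% | −19% | −8% |
| Brief, whole void | 10% | 1% | −7% | −9% | −6% |
| Until end press, 5 s initiation | 101% | 101% | 93% | 87% | 81% |
| Until end press, whole void | 99% | 97% | 95% | 91% | 86% |

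With brief text, five cycles gave the same values to within 1 percentage point.

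Setting B:
- Brief text, window timed from the instruction: about 40% (37% to 43% across runs).
- Brief text, window timed from flow: 37% at 0 s, 5% at 3 s, −6% to −13% at 6 to 20 s.
- Brief text, whole void: about −5% to +10%.
- Text until the end press, either window: about 91% to 105%.
- Leakage from the button press is small, about −11% to +7% of the press response.

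**Step 2, dependence on hesitancy.** In setting B with flow timing, prompt flow against a long delay differs by 37 − (−6) = 43 to 37 − (−13) = 50 percentage points of the text response. In setting A with text until the end press, the initiation window moves by 101 − 81 = 20 points. Timing from the instruction makes leakage nearly constant but does not remove it. Timing from flow without a text term makes it depend on delay. Both changes are therefore needed.

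**Step 3, cost of adding text and press regressors.** Regress v on both; VIF = 1/(1 − R²), and the standard error is multiplied by √VIF. Setting A:
- Brief text, 5 s window: VIF 1.99 at 0 s (√1.99 = 1.41), 1.32 at 2 s (1.15), 1.03 or less from 5 s (at most 1.01).
- Brief text, whole void: VIF at most 1.04 (1.02).
- Text until end press, 5 s window: VIF 1.11 to 1.30 (1.05 to 1.14).
- Text until end press, whole void: VIF 1.84 to 7.06 (1.36 to 2.66).

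In setting B the standard error widens by about 0% to 13% with brief text. With persistent text it widens by 10% to 23% for the initiation window, and by 44% to over 300% for the whole void.

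**The case against.** The strongest reply is that the plan is unspecific rather than shown to omit the cue. Its model is meant to contain the experiment's explanatory variables, which could include text and presses. The hold instruction is also projected text, so comparing void with cued hold could cancel part of the visual effect. Concurrent urodynamics are to be correlated with the fMRI data and could time the void. All of this is possible, but the plan commits to none of it.

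A reader might infer that reading activity has already been counted as bladder control. The documents do not support that: the authors label the occipital activity as stimulus-related, attribute nothing to reading, and attribute nothing on the map to the button press. A reader might also infer that the healthy women did the same task with the cue left in the model. The background describes neither the cues nor the model of that series. What stands is narrower: stimulus-related activity reached a list of voiding-initiation areas in this project, and the present plan states no safeguard.

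It is also fair that no single leakage figure can be defended, and that the cost of the remedy is not always small.

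**Conclusion.** The gap is real, and it is more than missing detail, because the project's own healthy results show the effect it leaves open. It is a risk, not a demonstrated error. Its size rests on text duration, void-onset definition and window length, which the documents do not state, and on the assumed timings. Across those assumptions the leakage runs from negligible or slightly negative (whole-void window with brief text, or an initiation window timed from late flow) to nearly complete (text on screen until the end press). For a 10 s window timed from the instruction with brief text it is about 40%; a 5 s window with immediate flow gives 88%. Where leakage changes with cue-to-flow delay, differences from the healthy data or between scans could arise from hesitancy alone. This should be settled before the maps are interpreted; it does not make the study uninterpretable.

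**What to change.** Amend Data Analysis to:

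1. State how long each text is displayed, and define void onset from the concurrent urodynamic trace.
2. Add to each woman's model a regressor for text display, with actual onsets and durations, and one for button presses. Onsets alone would not capture text that stays on screen.
3. Pre-specify the contrast, for example void versus text-cued hold, over and above cue and press. The final relax text is a weaker void-free event, since it appears at the finish press directly after voiding.
4. Report cue-to-flow delay per woman and scan, and the collinearity of the void regressor.
5. Refit the ten healthy scans the same way, where their event timings allow, before using them as the reference.

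This needs revised wording and refitting, with no extra scanning. The cost is precision. With brief text the standard error of the void effect widens by about 0% to 13% for a 10 s window, though by 41% for a 5 s window with immediate flow. With persistent text it widens by up to roughly 20% for an initiation window, but much more for a whole-void effect. In that last case, make the initiation window or the text-cued contrast the main estimate.
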